### **Study Setting**

For this study, public schools (boys and girls) in Gojra will be selected. There are 40 public schools (20 boys and 20 girls) in Gojra. We will invite the schools for study projects that fulfill the eligibility criteria (inclusion and exclusion criteria). From these willing schools, four public schools that are at least 1-2 Km away from each other (two boys and two girls) will be randomly selected via balloting. The inclusion criterion related to distance is intended to reduce contamination between schools of different arms. These four schools (boys and girls) will then be randomly assigned to either the school (one boy and one girl) with the intervention or to the school (one boy and one girl) without the intervention (Control school).

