**Detail of project activities**

Outline of the study
Formative Phase

Activities	Strategies	Target Population	Channels	Material
Formative assessment qualitative	Focus group discussions (FGDs)	
 
• Adolescents (6,7,8 grade)
 
• Teachers
 
• Mothers/immediate caretakers
 
	Researcher	FGD interview guide
	Key informant interview (KII)	School management	Researcher	Interview guide
	School document analysis	
 
• Curriculum of 6,7,8 grade
 
• School policy
 
	Researcher with teachers	Reviewing school curriculum, textbooks, and policy
RCT Phase				
Baseline assessment	Knowledge, attitude, and practices (KAP) assessment	Early school adolescents (6,7,8 grade)	Researcher	KAP survey questionnaire
	Anthropometric measurement (BMI)	Early school adolescents (6,7,8 grade)	Researcher	-Height scale -weight machine -WHO growth chart
	Micronutrient assessment (complete blood picture, Zinc and serum calcium, Vitamin D)	Adolescents sample (subset of 108 participants, 54 from each group)	LAB (AKU)	A blood test from Lab
	Physical assessment (skin, hair, eyes, nail, tongue, teeth, gums,)	Early school adolescents (6,7,8 grade)	Researcher	Check list
	Observation (Eating and WASH practices) at school	Early school adolescents (6,7,8 grade)	Researcher	Observation checklist
Intervention phase (Duration 4 months)				

Module development	Development of module on Nutrition and WASH component	For early adolescents (6,7,8 grade)	
 
• Research team
 
• Nutritionist
 
	
 
• Pakistan Dietary guideline
 
• WHO guidelines
 
• UNICEF guidelines
 
• Literature search
 

Workshop	2 workshops will be conducted for the school teachers	For School teachers (Teaching 6,7,8 grade)	Researcher	Based on the Module & teaching strategies
Deworming	Administering Deworming medicine to study participants	Early adolescents (6,7,8 grade)	School teachers	Tab Zentel
	Micronutrient supplementation to study participants	Early adolescents (6,7,8 grade)	School teachers	Micronutrient supplementation 1 tab daily for three months

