##### ***Baseline assessment***

Knowledge, attitude, and practices regarding nutrition and WASH will be assessed among school adolescents through a KAP survey along with anthropometric

measurement, physical assessment, and micronutrient assessment (CBC, Zinc, Calcium,).

The observation on the eating and WASH practices of grade 6-8 adolescents will be done by the researcher during break time (lunch time) and school off timings.

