### **Data collection tool/instrument**

Data will be collected through adopted and adapted self-administered, structured questionnaires from 6,7, and 8-grade school-going adolescents at baseline and the end line. The questionnaire will be categorized into four main groups to assess the respondent's demographic data and their knowledge, attitude, and practices (KAP) about nutrition and WASH. Group A (demographic characteristic), group B contains physical assessment, group C included 24 Questions on KAP on nutrition that are adopted from the KAP manual developed by the Food and Agriculture Organization of the United Nations (2014) and group D are based on the 16 WASH items adopted from GSHS version 2013. The questionnaire will be translated into the Urdu language. Observation of the eating practices, school canteen, WASH, and school environment will be assessed through a checklist at baseline and end line.

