### Data analysis plan

Quantitative variables will be described by means and standard deviations whereas median with interquartile range will be mentioned for qualitative variables. Frequencies and percentages will be calculated for the knowledge, attitude, and practices of adolescents regarding nutrition and WASH. The comparison between intervention and control at baseline and end line will be performed by using paired t-test and Chi-square. For the variables that are not normally distributed, a nonparametric test McNamara will be used. Binary logistic regression and multiple linear regression will be used to assess the effect of intervention. All the statistical analyses will be conducted using SPSS version 23. A p-value less than 0.05 will be considered statistically significant.

Descriptive	Inferential

 
• Mean, SD Normally distributed
 
• Median, interquartile range Skewed distribution
 
• Percentages and frequencies of knowledge, attitude, and practices
 
	
 
• Chi-Square-McNamara knowledge, attitude, and practices
 
• T- test paired Continuous variables
 
• Binary logistic regression and multiple linear regression
 
• Proportion changes - chi-square Observational checklist
 

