### **Post-intervention phase:**

A KAP questionnaire administered before intervention will be used to assess the changes in knowledge, attitude, and practices of school adolescents in the post-intervention phase. Anthropometric measurement, micronutrient assessment, and physical assessment will also be done to assess the effectiveness of the intervention. Moreover, the checklist will also use to evaluate the changes in the School environment and WASH practices.

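### Chi-square at p<0.05 is planned for the observation checklist, but its canteen and school-environment items appear to exist once per school, and two schools per arm cannot validly reach 0.05

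*Protocol*

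**What the plan says.** All references are to the protocol.

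- **Test.** The inferential column of the table in the Phase II Data analysis plan pairs "Proportion changes - chi-square" with the observational checklist. The text above the table sets the threshold: "A p-value less than 0.05 will be considered statistically significant". No exact or small-sample alternative is named for the checklist.
- **Content.** Data collection tool/instrument: "Observation of the eating practices, school canteen, WASH, and school environment will be assessed through a checklist at baseline and end line".
- **Use.** Post-intervention phase: "the checklist will also use to evaluate the changes in the School environment and WASH practices".
- **Pupil practices.** The same checklist also covers pupils. The table under Detail of project activities lists "Observation (Eating and WASH practices) at school" with grade 6-8 adolescents as the target population. Baseline assessment adds: "The observation on the eating and WASH practices of grade 6-8 adolescents will be done by the researcher during break time".
- **Number of schools.** Study Setting: "four public schools that are at least 1-2 Km away from each other (two boys and two girls) will be randomly selected via balloting", and then "These four schools (boys and girls) will then be randomly assigned to either the school (one boy and one girl) with the intervention". The other boys' school and the other girls' school are the controls.

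The protocol does not show the checklist, count its items, or say what one observation on it is.

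**The concern.** A canteen or a school environment is a property of a school. An item on either most naturally yields one value per school and round, so a comparison of arms rests on four values, two against two. The p-value of Pearson's chi-square comes from a large-sample approximation that cannot be trusted at that size. Here it errs towards declaring significance.

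The intervention is meant to act on the school environment (Framework, institution level; Intervention), and the results are to go to policymakers (Dissemination phase). A p-value below 0.05 that comes only from the approximation could then be read as evidence that school environments changed.

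Modelling pupils within schools would not repair these items, because they have no pupil-level data to model.

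**Working it through.** The protocol gives no figure for the checklist analysis, so there is none to reproduce.

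**Inputs.** Four schools, two per arm, one boys' and one girls' in each (Study Setting). Chi-square at 0.05 (Data analysis plan). One value per school for canteen and environment items (inferred).

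**1. Complete separation: item present in 2 of 2 intervention schools and 0 of 2 control schools.**

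- Pearson: N(ad − bc)² / (product of the margins) = 4 × (2×2 − 0×0)² / (2×2×2×2) = 64/16 = 4.00 on 1 df, p = 0.0455. All four expected counts equal 1.
- Yates-corrected: 4 × (4 − 2)² / 16 = 1.00, p = 0.317.
- Fisher's exact, two-sided: there are 6 ways to choose two schools of four, and 2 of them are as extreme, so p = 2/6 = 0.333.
- Randomisation test under the protocol's own allocation: 2 choices of boys' school × 2 of girls' school = 4 allocations. Two of them separate the schools completely, so p = 2/4 = 0.50.

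Complete separation is the most extreme result possible. These exact values are therefore the smallest attainable p-values, and no once-per-school item can reach 0.05.

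**2. The other informative patterns.** For 2/2 v 1/2: 4 × (2×1 − 0×1)² / (2×2×3×1) = 16/12 = 1.33, p = 0.248; Fisher's p = 1.0; expected counts 1.5 and 0.5. The pattern 1/2 v 0/2 gives the same p-values. Complete separation is thus the only pattern that the planned test calls significant.

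**3. How often this happens with no effect.** Let q be the chance that a school has the item, the same for all four schools and independent between them. Separation in either direction has probability 2q²(1 − q)².

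| Assumed prevalence q | False-positive chance per item |
|---|---|
| 50% | 2 × 0.25 × 0.25 = 12.5% |
| 30% or 70% | 2 × 0.09 × 0.49 = 8.8% |
| 20% or 80% | 2 × 0.04 × 0.64 = 5.1% |
| 10% or 90% | 2 × 0.01 × 0.81 = 1.6% |

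**4. If the row means baseline against end line within one arm.** Two schools without the item before and with it after give the same 2×2 table and the same Pearson p of 0.0455. The pairing is then ignored as well. An exact paired test on two schools that both change the same way gives 2 × (1/2)² = 0.50.

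**The case against.** The strongest reply is that the unit is inferred. The activity tables and the baseline text describe the observation of pupils, and a change in proportions fits counts of pupils better than two schools out of two. Only Data collection tool/instrument and Post-intervention phase bring in the canteen or the school environment. This stands as a limit: the protocol does not say that chi-square will be run on four values. It does not remove the point, because those items are on the checklist and the table gives the whole checklist one test. Reading every item as a pupil count does not rescue chi-square either, since pupils observed in two whole schools per arm are not independent. That is the general clustering problem of this design. It is not sized here, because the protocol gives neither the number of pupils observed nor an intraclass correlation.

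A second reply is that a Yates correction gives p=0.317 and removes the false positive. That is true, but the plan names plain chi-square.

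A third is that such details belong in a statistical analysis plan. The protocol has already named the test, however.

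A reader might infer more than the documents support:

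- **That every expected count is at most 1.** This holds only when exactly two schools have the item. With one or three, the counts are 0.5 and 1.5.
- **That a large overall false-positive rate can be stated for the checklist.** The number of items is not given, and items within one school are unlikely to be independent. The eligibility criteria also require working WASH facilities, so some items may be present in almost every school, where the rate falls to 1.6% or less.
- **That pupils are counted repeatedly within a round.** The protocol is silent on how observed pupils are identified, and silence does not show this.

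**Conclusion.** The point holds for the once-per-school items. The test named for them would call complete separation significant at p=0.046, although the exact value is 0.33, or 0.50 under the sex-matched allocation. This rests on two assumptions: that canteen and environment items yield one value per school, and that the uncorrected statistic is used as written. How often a false positive would arise depends on the assumed prevalence: it is well above 5% for items present in 30% to 70% of schools, about nominal at 20% or 80%, and below nominal at 10% or 90%.

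It would go too far to say that the trial's main conclusion is at risk. The checklist is not among the four assessments under Outcome of the study, nor in the objectives. Practices are measured as an outcome by the KAP questionnaire, and the protocol does not say that any conclusion will rest on checklist p-values. The row should be corrected, but it is a defect in a supporting analysis.

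**What to change.** Replace the checklist row in the inferential table with wording such as: *Observational checklist: descriptive. Items recorded once per school are shown for each of the four schools at baseline and end line, without p-values. Observed pupil eating and WASH practices are summarised as a percentage per school and round, and are not tested by a chi-square that treats pupils as independent of school.* State in Data collection tool/instrument which items are recorded per school and which per pupil.

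The cost is one table row and one sentence. The downside is that no p-value is claimed for a supporting measure outside the four listed outcome assessments. For the once-per-school items nothing valid is lost, because four schools cannot support a test at 0.05.

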### Intervention Phase

**Study participants**

Early adolescents studying in 6,7, and 8 grades in selected public schools of Gojra and school teachers who are teaching 6-8 grade students.

**Intervention**

The intervention will be planned based on a socio-ecological model and health-promoting school framework. School health environment, health education, health services, and nutrition programs will be focused in the intervention stage of the study.

Based on the formative assessment, the module will be developed in consultation with Nutritionist, the research team, and recent literature. For the validity of the module, expert opinions will be taken from the nutritionist, school education, and WASH experts. Two to three workshops will be arranged for school teachers to train them as master trainers who are teaching 6 to 8-grade school-going adolescents. Sixteen sessions (one session per week) will be arranged on nutrition education and water, sanitation, and hygiene for adolescents. Micronutrient tablets will be administered to adolescents for three months daily through school teachers. Moreover, 6-8 grade adolescents will be dewormed before and after the intervention. In addition, Cooking recipes in the local language will be shared with the adolescent's mother/immediate caretakers through adolescents. Different strategies will be used in the study sessions like demonstrating and showing videos on hand washing, role play, quiz etc.

During the intervention phase, there are no such risks involved to the study participants except their valuable time. Due to deworming and micronutrient supplementation, there may be temporary dizziness, nausea, headache, constipation, and dark color stool along with discomfort from prick for blood drawing from adolescents. To reduce the temporary side effects of deworming administration, the researcher will advise them to keep adequately hydrated themselves and take the micronutrient supplementation tablet. Reassurance regarding drawing

the blood samples will be done. The existing referral system will be identified and utilized if needed

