## Summary

Globally, one of the major risk factors for adolescent morbidity is considered Malnutrition. Worldwide adolescent age group 10-19 is increasing and they are at increased risk of malnutrition-related diseases resulting in high morbidity and mortality. Asian countries are suffering from the double burden of malnutrition including Pakistan. The risk factors that contribute to malnutrition in the population include unsafe drinking water, poor sanitary conditions, lack of proper waste disposal facilities, poor health awareness, and poor nutrition and hygiene. However, studies have shown that nutrition education, and water, sanitation, and hygiene (WASH) programs in schools are effective strategies to promote the health status of adolescents (girls and boys). The primary objective of this study is to determine a school-based nutrition and WASH education intervention to improve nutritional status among early adolescents. The randomized control trial (RCT) study design will be chosen for this study. This study will be carried out in Gojra public schools, in Punjab. The study participants will be 6-8 grade school-going adolescents (girls and boys), their mothers/immediate caretakers, and school teachers. The data collection methods that will be used for the study are surveys, focus group discussions (FGDs), and through observation. Anthropometric measurements and specified micronutrient levels of adolescents will be measured at baseline and end line. The intervention will consist of skill-based nutrition and WASH education for the adolescents along with deworming and micronutrient supplementation. Workshops based on nutrition and WASH will be arranged for school teachers. This study will be carried out over one year with two-time data collection (baseline, and end line). Data will be analyzed by using SPSS and transcription. The expected outcome of the study would be that the implementation of identified nutrition and WASH strategy is effective to generalize in the poor nutritional status population in schools. It will show the promising benefit of education and WASH intervention, in reducing the cases of

early adolescent malnutrition. Through the findings of the study, we can bring the revolution at the micro-level targeting the community to modify the curriculum of this age group.

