## Introduction

Malnourishment is one of the grave public health issues and a significant cause of high morbidity and mortality among young Pakistani children. Several factors determine the high prevalence of malnutrition, which includes unsafe drinking water, poor sanitary conditions, lack of proper waste disposal facilities, poor health awareness, and poor nutrition and hygiene (Hirani, 2012). According to a report by the World Health Organization (WHO) published in 2017, malnutrition was categorized into three broad groups; “**undernutrition** (wasting, stunting, and underweight), **micronutrient related malnutrition** (deficiency or excess of micronutrients), **overweight, obesity and diet-related non-communicable diseases**” (Dat, 2018). According to another report by WHO, which was based on anthropometry, nutrition was classified as under and over-nutrition. According to this classification, **undernutrition** is divided into thinness, stunting, and underweight, while **overnutrition** is grouped into overweight and obesity. This classification of malnutrition was for children over five and adolescents. (De Onis, 2015).

At present, adolescents constitute the major proportion of all the age groups worldwide and 1.8 billion of the total world population consists of adolescents (between 10-19 years of age). Out of these, approximately 90 percent belong to Low and Middle-Income countries (LMICs) (Patton & Kabir, 201, Christian, 2018). The adolescent population was further divided into early and late adolescent by United Nations, the early adolescents age range between 10–14 years, and the late adolescents age group range between 15– 19 years (Christian, 2018).

In 2015, about 1.2 million adolescent deaths occurred globally (WHO,2017), 26 % of them in the South East Asian Region (WHO,2016). The leading causes of death in early adolescents include diarrheal diseases, intestinal infections and respiratory tract infections, and road traffic accidents (Dick, 2015). Malnutrition is the major contributing factor coupled with other causes of adolescent death (Reiner,2019). Globally, the main nutritional issues affecting

adolescents are undernutrition, anemia, and micronutrient deficiencies (Iron, Vitamin A, Zinc, and iodine,) (Shahid, 2009). Around 1.2 million adolescents in developing countries face serious nutritional challenges (Hossain, 2017 & Akhter, 2013).

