### **Activities of baseline assessment**

Activities	Purpose	Frequency
KAP survey	To know the KAP regarding nutrition and WASH	Baseline and end line
Anthropometric measurements	To identify the number of thin, underweight, Overweight, and Obese adolescents in 6-8 grade	Baseline and end line
Physical assessment	To identify the health status of adolescents	Baseline and end line

Monitoring CBC, Zinc, Calcium, and Vitamin D level	To identify the deficiency of micronutrients at baseline and improvement at the end line	Baseline & end line
Observations	To assess the practices related to major determinants of malnutrition i.e. nutrition, water, sanitation, and hygiene.	Baseline & end line

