**Ethical consideration**

Study Approval will be obtained from the Aga Khan University Ethical Review Committee (ERC). Approval will also be sort from the participating school management in Gojra. Anonymity, confidentiality, and respect for human dignity are the main concerns in any of research addressing behaviors (Polit & Beck, 2008). Any identification information like name and personnel information will be replaced by codes to address anonymity issues. Confidentiality of the data will be ensured by keeping the data under safe custody, electronic files will also be password protected. Only the primary investigator will access the raw data and the research team members involved in data analysis. Respect for human dignity will be safeguarded by completely informing the participants about all aspects of the study including purpose, their rights including the right to withdraw from the study at any point, and all possible risks and benefits. This information will be communicated verbally as well as in writing in the form of consent /assent. For the adolescent's participation, assent will be obtained after taking permission from their parents / immediate caretaker. The trial will be conducted in compliance with the protocol, GCP, and the applicable regulatory requirement(s).

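### The Intervention section denies any risk and then names side effects, and no listed outcome, instrument or analysis records those side effects in either arm

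*Protocol*

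**What the plan says.** The Intervention section (Phase II) states that, during this phase, "there are no such risks involved to the study participants except their valuable time". The sentence that follows says that, because of deworming and supplementation, "there may be temporary dizziness, nausea, headache, constipation, and dark color stool along with discomfort from prick for blood drawing from adolescents". The planned response is advice from the researcher, reassurance about the blood draw, and use of an existing referral route where required.

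The exposure is a daily micronutrient tablet for three months, handed out by teachers, and deworming before and after the intervention. Sample Size & Sampling Strategy plans 180 pupils per arm, with blood samples from 54 per arm. The material for the teacher workshops is described as "Based on the Module & teaching strategies".

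Ethical consideration promises that participants will be told of every possible risk. The Summary expects to find that "implementation of identified nutrition and WASH strategy is effective to generalize", and the dissemination phase sends recommendations to policymakers.

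**The concern.** Two adjacent sentences cannot both stand. The participants are minors, and their assent and their caretakers' consent depend on a correct statement of risk, so the protocol should carry one consistent account.

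The second problem is what the trial can report. The protocol expects certain symptoms from the drug and the tablet, but the listed measurements serve effectiveness only. If symptoms are never written down, no analysis plan can recover them. A reader deciding whether to adopt the package in schools would learn about BMI, bloods and knowledge, and nothing about how often pupils had the effects that the protocol foresaw.

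**Working it through.** The protocol gives no figure on this point to reproduce. The check is whether any listed step would record dizziness, nausea, headache, constipation, dark stool or discomfort from the blood draw.

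| Place in the protocol | What is listed | Records the named effects? |
|---|---|---|
| Outcome of the study; Dependent variables | BMI, micronutrients, physical examination (for signs of deficiency), KAP | No |
| Detail of project activities, baseline and end line | KAP survey, BMI, bloods, physical checklist, observation of eating and WASH | No |
| Detail of project activities, intervention rows | Module, workshops, deworming, tablets, education, food log books | No |
| Data collection tool/instrument | Group A demographics, B physical assessment, C 24 nutrition items, D 16 WASH items | No symptom group named |
| Activities of baseline assessment | Same measures, with their purposes | No |
| Post-intervention phase | Same measures, to judge effectiveness | No |
| Data analysis plan (Phase II) | Descriptive summaries, paired t-test, chi-square, regression | No side-effect variable |
| Intervention, risk paragraph | Advice, reassurance, referral | A response, not a record |

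The count of listed steps that record the named effects is 0.

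**What recording would give.** Inputs: 180 treated pupils (Sample Size & Sampling Strategy), one-sided 95% confidence, pupils treated as independent.

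- Upper bound on a symptom's rate when none is seen: 1 − 0.05^(1/180) = 0.0165, or 1.65%. The rule of three gives 3/180 = 1.67%.
- Chance of seeing at least one case of a symptom with a true rate of 1%: 1 − 0.99^180 = 0.84.
- Comparison of arms, 180 per arm, two-sided 5%, 80% power. The protocol gives no background symptom rates, so I assume a range: control rates of 2%, 5% and 10% would allow detection of about 9%, 14% and 21% in the intervention arm.

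Each arm has only two schools (Study Setting), so all three results are optimistic.

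**Timing of recall.** Tablets run for 3 months of a 4-month intervention, and the end-line phase lasts 2 months. If dosing starts with the intervention, the last tablet falls 4 − 3 = 1 month before it ends. A pupil assessed at the close of the end-line phase would then be asked 1 + 2 = 3 months after the last tablet. The gap therefore runs from about 0 to 3 months, depending on schedules the protocol does not fix.

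**The case against.** The best defence is that the questionnaire items are not shown. The protocol says that the survey will cover adolescent health status, and gives the physical assessment a similar purpose, so a symptom question could exist. That is fair as a caution. But the four questionnaire groups are described by content, and none is a symptom group. The physical examination is tied to signs of deficiency. The point stands for what the protocol lists.

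The intervention is also to be finalised after the formative phase, and the workshop description does not exclude a session on reactions. This stands too: the protocol does not rule out recording. It simply contains no such step.

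A reader might infer four stronger things that the document does not support.

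- **That the trial has no harm data at all.** Blood counts, BMI classes including overweight and obesity, and the physical examination are collected in both arms and could show some unintended effects. The gap concerns the effects that the protocol names.
- **That a micronutrient level pushed above range would be scored as benefit.** The Introduction's definition of malnutrition includes "deficiency or excess of micronutrients", and the bloods are taken "To identify the deficiency of micronutrients at baseline and improvement at the end line". The latter is a purpose, not a scoring rule. The secondary objective speaks of levels, cut-offs may sit in an analysis plan not shown, and the tablet's content is not given.
- **That the promise of GCP compliance is broken.** The protocol does not say what that standard requires here, so the argument would rest on an outside source.
- **That families are told there is no risk.** The consent and assent forms are not available to this review, and Ethical consideration commits to disclosure.

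Finally, the Summary's phrase about generalising refers to the nutrition and WASH strategy, not to the tablets by name. That weakens any claim that the trial will recommend supplementation, but the effect it reports will still be that of the whole package.

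**Conclusion.** The point holds in two parts. The risk statement in the Intervention section contradicts the sentence after it. And no listed outcome, instrument or analysis captures the side effects named there, in either arm, so the trial as written gives no tolerability estimate for them. With recording, the planned 180 treated pupils could bound an unseen symptom's rate at about 1.65%, given full follow-up and independence between pupils; two schools per arm make that optimistic. Without recording, no bound can be given.

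The conclusion assumes that the questionnaire holds no symptom items beyond the groups described. This is a cheap improvement that should be made. It does not affect the validity of the effectiveness comparison.

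**What to change.** 1. Reconcile the sentence denying risk with the list that follows, so that the risks disclosed to families match the protocol.
2. Add the same short set of items on the named symptoms, with the same stated recall period, to the baseline and end-line questionnaires in both arms, and report counts by arm. Fix the end-line date relative to the last tablet, because the gap could otherwise reach about three months. Teachers in the intervention arm may also keep a symptom line during tablet dosing. Report that line descriptively only: the control arm would have no matching record, and an end-line recall question cannot supply the background rate for it.
3. Use part of a planned teacher workshop to cover how a reaction is recorded and to which role it is reported.
4. Optionally, tabulate by arm the number of values above the laboratory's upper reference limit in the 54 + 54 blood samples already planned, since the Introduction counts excess as a form of malnutrition.

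The cost is a few questionnaire items, part of an existing workshop and one extra table, with no new visits or blood tests. The questionnaire becomes slightly longer, and the symptom data will be crude, unblinded and recalled.
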